#### 5. SAMPLE SIZE JUSTIFICATION

Up to consideration adult male and female subjects (women of non-childbearing potential only) will be enrolled. The sample size chosen for this study was selected without statistical considerations, but is consistent with previous studies of a similar design. Up to consideration are anticipated to be sufficient to provide a reliable estimate of the magnitude and variability of the interaction. Replacement subjects may be enrolled only if deemed necessary by the Sponsor. Every attempt will be made to enroll at least 4 subjects of each sex in the study.

#### 6. STUDY TREATMENTS

The study treatment sequence name and ordering to be used in the TFLs are presented in Table 1.

**Table 1: Presentation of Study Treatment Sequence in TFLs** 

Study Treatment Sequence	Order in TFLs
0.5 mg repaglinide alone/200 mg LOXO-305 QD alone/200 mg LOXO-305 QD + 0.5 mg repaglinide	1

The study treatment names, abbreviations, and ordering to be used in the TFLs are presented in Table 2.

**Table 2: Presentation of Study Treatments in TFLs** 

Study Treatment	Order in TFLs (PK)	Order in TFLs (all others)
0.5 mg repaglinide alone	1	1
200 mg LOXO-305 QD alone	3	2
200 mg LOXO-305 QD + 0.5 mg repaglinide	2	3

All treatments described above are the planned treatments. The TFLs will reflect the actual treatments received

#### 7. DEFINITIONS OF POPULATIONS

Any protocol deviations, including those related to SARS-CoV-2 (COVID-19), will be considered prior to database lock for their importance and taken into consideration when assigning subjects to populations.

# 7.1. All Subjects Population

The all subjects population will include all subjects who signed the ICF and had any study assessment recorded in the database per the protocol.

# 7.2. Safety Population

The Safety Population will include all subjects who received at least 1 dose of study drug (repaglinide and/or LOXO-305). Subjects will be classified into groups based on actual treatment received.

#### 7.3. Pharmacokinetic Population

The PK Population will include all subjects who received a dose of LOXO-305, have at least 1 quantifiable plasma concentration, and for whom at least 1 PK parameter can be computed. A subject may be excluded from the PK summary statistics and statistical analysis if the subject has an AE of vomiting that occurs at or before 2 times median  $t_{max}$  for the analyte being evaluated. The impact of protocol deviations on PK population will be evaluated on a case-by-case basis.

#### 8. STATISTICAL METHODOLOGY

#### 8.1. General

Listings will be provided for all data captured in the database. Listings will include all subjects assigned to the all subjects population and include data up to the point of study completion or discontinuation. Subjects are generally considered to have completed the study if they completed all protocol-specified procedures and assessments for the EOT visit. Any subject who discontinued the study will be identified accordingly in the listings. Summaries and statistical analyses will include the subjects assigned to the relevant population based on data type.

Data analysis will be performed using the SAS® statistical software package Version 9.4 (or higher if upversioned during the study).

Analysis Data Model (ADaM) datasets will be prepared using Clinical Data Interchange Standards Consortium (CDISC) ADaM Version 2.1 (or higher if upversioned during the study) and CDISC ADaM Implementation Guide Version 1.2 (or higher if upversioned during the study). Pinnacle 21 Community Validator Version 2.2.0 (or higher if upversioned during the study) will be utilized to ensure compliance with CDISC standards.

Caution should be used when interpreting results from the statistical analyses conducted in this study because the sample size is not based on power calculations.

Where reference is made to 'all calculations', this includes, but is not limited to, summary statistics, statistical analyses, baseline derivation, changes from baseline, and any parameter derivations.

#### 8.1.1. Calculation of the Summary Statistics

For continuous data the following rules will be applied:

- Missing values will not be imputed, unless specifically stated otherwise.
- Unrounded data will be used in the calculation of summary statistics.
- If the number of subjects with valid observations (n) <3, summary statistics will not be calculated, with the exception of n, minimum, and maximum.
- As ET data is not associated with any scheduled timepoint, it will be excluded from all calculations of summary statistics.
- Post dose repeats and unscheduled assessments will not be included in calculation of summary statistics.

For categorical data the following rules will be applied:

- If the categories of a parameter are ordered (eg, AE severity), all categories between the possible minimum and maximum categories will be included, even if n = 0 for a given category. If the categories are not ordered (eg, race), only those categories for which there is at least 1 subject represented will be included.
- Missing values will not be imputed, with the exception of AEs where the 'worst-case' approach will be taken (see Section 8.6.1), or unless specifically stated otherwise. A 'missing' category will be included for any parameter for which information is missing. This will ensure that the population size totals are consistent across different parameters.

All protocol deviations and data issues (eg missing data, out of protocol window) that occur during the study, including those related to COVID-19, will be considered prior to database lock for their severity/impact on how the data will be displayed.

#### 8.1.2. Repeat and Unscheduled Readings

For vital sign measurements and 12-lead ECG data only, any predose value recorded in addition to the original value or a postdose value recorded within 15 minutes of the original value will be defined as a repeat value; any postdose value recorded more than 15 minutes after the original value will be defined as an unscheduled value. For all other data types (eg, laboratory values), any value recorded in addition to the original value will be defined as an unscheduled value.

The original scheduled value will be used in all calculations post dose. In the event of any repeats or unscheduled measurements taken pre-dose the values will be considered when determining the baseline value.

Post dose repeats, unscheduled assessments, and ET measurements will be excluded from all calculations, with the exception of the baseline derivation (see Section 8.1.3).

#### 8.1.3. Definitions of Baseline and Change from Baseline

Baseline value is defined as the last non missing measurement before administration of study drug on Day 1.

If the date/time of the value is incomplete or missing, it will be excluded from the baseline calculation, unless the incomplete date/time indicates the value was recorded prior to dosing of study drug.

Individual changes from baseline will be calculated by subtracting the individual subject's baseline value from the value at the timepoint. The mean change from baseline will be defined as the mean of the individual changes from baseline for all subjects.

See Section 8.1.2 for more detail on handling repeat and unscheduled readings in the calculations.

#### 8.2. Subject Disposition and Population Assignment

Subject disposition and population assignment will be listed.

A summary table by treatment sequence will be provided, based on the all subjects population.

# 8.3. Demographics and Baseline Characteristics

The screening demographics and baseline characteristics including age, sex, race, ethnicity, height, body weight, and body mass index will be listed.

A summary table by treatment sequence will be provided, based on the safety population.

#### 8.4. Prior and Concomitant Medication

Prior medication will be defined as medication that ends prior to the first dose of Repaglinide. Concomitant medication will be defined as medication that starts during or after the first dose or starts but does not end prior to the first dose.

Prior and concomitant medications will be coded using the World Health Organization Drug Dictionary (WHODrug) Global, Format B3, Version September 2020. Prior and concomitant medications will be listed.

#### 8.5. Pharmacokinetic Assessments

### 8.5.1. Pharmacokinetic Analysis

The following PK parameters will be determined where possible from the plasma concentrations of LOXO-305 and repaglinide using noncompartmental methods in validated software program Phoenix WinNonlin (Certara, Version 8.1 or higher):

**Repaglinide**; following a single dose of repaglinide alone (Day 1) and in combination with multiple doses of LOXO-305 (Day 12)

Parameter	Unitsa	Definition
AUC 0-t	h*ng/mL	area under the concentration-time curve from hour 0 to the last measurable concentration $(t_{last})^b$
$AUC_{0\text{-}inf}$	h*ng/mL	area under the concentration-time curve from hour 0 extrapolated to infinity c
$\%AUC_{extrap}$	%	percentage extrapolation for AUC 0-inf
$C_{\text{max}}$	ng/mL	maximum observed concentration
$t_{max}$	h	time to maximum observed concentration
$\lambda_{\mathrm{z}}$	1/h	apparent terminal elimination rate constant
$t_{1/2}$	h	apparent terminal elimination half-life
CL/F	L/h	apparent systemic clearance
V z /F	L	apparent volume of distribution

<sup>a Units are based on concentration units (provided by the bioanalytical lab or preferred units for presentation of PK parameters) and dose units used in the study.

**LOXO-305**; following daily multiple doses of LOXO-305 and a single dose of repaglinide (Day 12)

Parameter	Unitsa	Definition
AUC 0-t	h*ng/mL	area under the concentration-time curve from hour 0 to the last measurable concentration $(t_{last})^b$
$AUC_{tau}$	h*ng/mL	area under the concentration-time curve during a dosing interval
$C_{\text{max}}$	ng/mL	maximum observed concentration

<sup>b Area under the concentration-time curve will be calculated using the linear trapezoidal rule for increasing and decreasing concentrations.

<sup>c Based on the last observed quantifiable concentration

$C_{\text{trough}}$	ng/mL	concentration observed at the end of the dosing interval
$t_{\text{max}}$	h	time of the maximum observed concentration
CL ss /F	L/h	apparent systemic clearance at steady state

<sup>a Units are based on concentration units (provided by the bioanalytical lab or preferred units for presentation of PK parameters) and dose units used in the study.

Additional PK parameters may be determined where appropriate.

PK analysis will be carried out where possible using actual blood sampling times postdose. If an actual time is missing, the sample concentration result will be treated as missing unless there is scientific justification to include the result using the nominal time.

The parameters  $C_{max}$  and  $t_{max}$  will be obtained directly from the concentration-time profiles. If  $C_{max}$  occurs at more than 1 timepoint,  $t_{max}$  will be assigned to the first occurrence of  $C_{max}$ .

# 8.5.1.1. Criteria for the Calculation of Apparent Terminal Elimination Rate Constant and Half-life

The start of the terminal elimination phase for each subject will be defined by visual inspection and generally will be the first point at which there is no systematic deviation from the log-linear decline in concentrations.

The apparent terminal elimination rate constant ( $\lambda_z$ ) will only be calculated when a reliable estimate can be obtained using at least 3 data points, preferably not including  $C_{max}$ , and the adjusted coefficient for determination of exponential fit ( $R^2$ -adj) of the regression line is  $\geq 0.7$ . Parameters requiring  $\lambda_z$  for their calculation (eg,  $AUC_{0\text{-inf}}$ ,  $t_{1/2}$ , CL/F, and  $V_z/F$ ) will only be calculated if the  $R^2$ -adj value of the regression line is  $\geq 0.7$ .

The following regression-related diagnostic PK parameters will be determined, when possible:

Parameter Units Definition		Definition
$\lambda_z$	1/h	apparent terminal elimination rate constant
$\lambda_z$ Upper	h	end of exponential fit
$\lambda_z$ Lower	h	start of exponential fit
$\lambda_z N$	NA	number of data points included in the log-linear regression
$\lambda_z$ Span Ratio	NA	time period over which $\lambda_z$ was determined as a ratio of $t_{1/2}$
R  -adj	NA	adjusted coefficient for determination of exponential fit

Where possible, the span of time used in the determination of  $\lambda_z$  (ie, the difference between  $\lambda_z$  Upper and  $\lambda_z$  Lower) should be  $\geq 2$  half-lives. If the  $\lambda_z$  Span Ratio is  $\leq 2$ , the robustness of the  $t_{1/2}$  values will be discussed in the CSR.

<sup>b Area under the concentration-time curve will be calculated using the linear trapezoidal rule for increasing and decreasing concentrations.

# 8.5.1.2. Criteria for Calculation and Reporting of Area Under the Concentration-time Curve

The minimum requirement for the calculation of area under the concentration-time curve (AUC) will be the inclusion of at least 3 consecutive concentrations above the lower limit of quantification. If there are only 3 consecutive concentrations, at least 1 should follow  $C_{max}$ .

If the extrapolated area for  $AUC_{0-inf}$  is >30%,  $AUC_{0-inf}$  (and derived parameters) will be excluded from the summary statistics and statistical analysis at the discretion of the sponsor or pharmacokineticist.

If  $AUC_{0-inf}$  cannot be determined reliably for all subjects and/or treatments, an alternative AUC measure, such as AUC to a fixed time point or  $AUC_{0-t}$ , may be used in the statistical analysis.

# **8.5.1.3.** Criteria for Handling Below the Limit of Quantification or Missing Concentrations for Pharmacokinetic Analysis

Plasma concentrations below the limit of quantification (BLQ) will be assigned a value of 0 before the first measurable concentration and thereafter BLQs will be treated as missing. The following rules apply with special situations defined below:

- If an entire concentration-time profile is BLQ, it will be excluded from PK analysis.
- Where 2 or more consecutive concentrations are BLQ at the end of a profile, the profile will be deemed to have terminated and any further quantifiable concentrations will be set to missing for the calculation of the PK parameters, unless they are considered to be a true characteristic of the profile of the drug.
- If a Day 1 or Day 12 predose repaglinide plasma concentration is missing, it may be set to zero by default. If a Day 12 predose concentration of LOXO-305 is missing, the concentration at 24 hours may be used as the predose value.

#### 8.5.1.4. Treatment of Outliers in Pharmacokinetic Analysis

If a value is considered to be anomalous due to being inconsistent with the expected PK profile, it may be appropriate to exclude the value from the PK analysis. However, the exclusion of any data must have strong justification and will be documented in the CSR.

Any quantifiable predose concentration value for repaglinide on Days 1 or 12 will be considered anomalous and set to missing for the PK analysis.

#### 8.5.2. Presentation of Pharmacokinetic Data

Individual concentrations deemed to be anomalous will be flagged in the listings and excluded from the summary statistics.

For PK concentration data the following rules will apply:

- Values that are BLQ will be set to 0 for the calculation of summary statistics.
- Arithmetic mean or median values that are BLQ will be presented as 0.
- If any BLQ results (treated as 0) are in a series of summarized data, geometric mean (Geom Mean) and coefficient of variation (CV) of geometric mean will be reported as not calculated (NC).

For PK parameters the following rule will apply:

• Geom Mean and CV will not be calculated for tmax.

#### 8.5.3. Pharmacokinetic Statistical Methodology

All PK concentrations and parameters will be listed.

Summary tables, mean (+ standard deviation [SD]) figures, overlaying individual figures, and individual figures by treatment and time postdose will be provided for plasma PK concentrations. All PK concentration figures will be produced on both linear and semilogarithmic scales, with the exception of figures across all days, which will be produced on the linear scale only. The +SD bars will only be displayed on the linear scale.

Summary tables by treatment will be provided for all PK parameters, with the exception of diagnostic regression-related PK parameters. Summary statistics (n, Mean, SD, CV, minimum, median, maximum, Geom Mean and geometric CV [Geom CV]) will be calculated for plasma LOXO-305 and repaglinide PK parameters. Excluded subjects will be listed in the PK parameter tables, but will be excluded from the statistical analysis and summary statistics and noted as such in the tables.

#### 8.5.3.1. Statistical Analysis

A statistical analysis will be conducted to investigate the drug-drug interaction of LOXO-305 on repaglinide for  $AUC_{0-t}$ ,  $AUC_{0-inf}$ , and  $C_{max}$ . The comparisons of interest are:

To assess the impact of multiple oral doses of LOXO-305 on the single dose PK of repaglinide (AUC0-t, AUC0-inf, and  $C_{max}$ )

• 200 mg LOXO-305 co-administered with 0.5 mg repaglinide (Day 12) (test treatment) vs 0.5 mg repaglinide (Day 1) (reference treatment).

The natural log (ln) transformed PK parameters (AUC0-t, AUC0-inf, and Cmax) will be analyzed using a mixed model. The model will include actual treatment as fixed effect, and subject as a random effect.

For each PK parameter separately, the least squares mean (LSM) for each treatment, difference in LSMs between the test and reference treatments, and corresponding 90% confidence interval (CI) will be calculated; these values will then be exponentiated to give the geometric least squares mean, geometric mean ratios, and corresponding 90% CI.

Additionally, the pooled estimate (across all treatments) of the within-subject CV will be calculated, and residual plots will be produced to assess the adequacy of the model(s) fitted.

# **Mixed Model Analysis**

```
proc mixed data = <data in>;

class treatment usubjid;
model lpk = treatment / cl residual ddfm = kr;
lsmeans treatment / cl pdiff = control('1') alpha = 0.1;
random intercept / subject = usubjid;
ods output lsmeans = <data out>;
ods output diffs = <data out>;
ods output covparms = <data out>;
run;
```

#### 8.6. Safety and Tolerability Assessments

#### 8.6.1. Adverse Events

All AEs will be coded using the Medical Dictionary for Regulatory Activities (MedDRA) Version 23.1. All AEs will be assigned severity grade using National Cancer Institute Common Terminology Criteria for Adverse Events (CTCAE) Version 5.0.

A treatment-emergent adverse event (TEAE) will be defined as an AE that starts during or after the first dose repaglinide, or starts prior to the first dose and increases in severity after the first dose.

A treatment-related TEAE will be defined as a TEAE with a relationship of related to the study treatment, as determined by the investigator.

If deemed related to study treatment, the assignment of TEAEs to treatments will be as follows:

- A TEAE occurring during or after Day 1 dosing and prior to Day 2 dosing will be assigned to 0.5 mg repaglinide
- A TEAE occurring during or after Day 2 dosing and prior to Day 12 dosing will be assigned to 200 mg LOXO-305
- A TEAE occurring during or after Day 12 dosing will be assigned to 200 mg LOXO-305 + 0.5 mg repaglinide

All AEs will be listed. In addition to the data recorded in the database, the listings will include derived onset time and duration. Onset time will be calculated from the time of the last dose for TEAEs only.

The frequency of subjects with TEAEs and the number of TEAEs will be summarized for the following categories:

• TEAEs (overall, serious, leading to discontinuation, and leading to death) by treatment

- TEAEs by severity and treatment
- Treatment-related TEAEs (overall, serious, leading to discontinuation, and leading to death) by treatment
- Treatment-related TEAEs by severity and treatment

The frequency of subjects with TEAEs will be summarized separately for all TEAEs and treatment-related TEAEs by the following:

- System organ class, preferred term, and treatment
- Preferred term and treatment

For the AE data the following rules will apply:

- For the derivation of TEAE status: If the start date/time of an AE is incomplete or missing, an AE will be assumed to be a TEAE, unless the incomplete start date/time or the end date/time indicates an AE started prior to the first dose.
- For the derivation of treatment-related TEAE status: If the study treatment relationship for a TEAE is missing, a TEAE will be assumed to be a treatment-related TEAE.
- For the derivation of onset time: If the start date/time of an AE is missing, onset time will not be calculated. If the start date/time of an AE is incomplete, where possible, the minimum possible onset time will be calculated and presented in '≥DD:HH:MM' format (eg, if the date/time of the last dose is 01MAY2019/08:00 and recorded start date/time of an AE is 03MAY2019, then the minimum possible onset time will be calculated by assuming the AE started at the first hour and minute of 03MAY2019 [03MAY2019/00:00], thus will be presented as onset time ≥01:16:00 in the listing).
- For the derivation of duration: If the end date/time of an AE is missing, duration will not be calculated. If the start or end date/time of an AE is incomplete, where possible, the maximum possible duration will be calculated and presented in '≤DD:HH:MM' format (eg, if the start of an AE date/time is 01MAY2019/08:00 and its recorded end date/time is 03MAY2019, then the maximum possible duration will be calculated by assuming the AE ended at the last hour and minute of 03MAY2019 [03MAY2019/23:59], thus will be presented as duration ≤02:15:59 in the listing).
- For the calculation of summary statistics: If the severity of a TEAE is missing, a TEAE will be counted under the maximum severity possible, up to Grade 4 in the absence of a fatal outcome.
- For the calculation of summary statistics: If a subject experienced multiple TEAEs with the same preferred term for the same treatment, this will be counted as 1 TEAE for that treatment under the maximum severity recorded.

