- c. Height collected at Screening only, body mass index based on Screening height.
- d. A complete physical examination will be performed at Check-in (Day -1) and an abbreviated physical examination will be performed at EOT (Day 16) or ET.
- e. The 12-lead ECGs will be obtained at Screening and Check-in (Day -1), Day 1 (predose), Day 2 (predose, 2 hours after LOXO-305 dosing), Day 6 (predose and 2 hours after LOXO-305 dosing), Day 12 (predose, and 2 hours after LOXO-305 and repaglinide dosing), and EOT (Day 16, ie, 96 hours after LOXO-305 and repaglinide dosing on Day 12) or ET. When scheduled at the same time as blood draws, 12-lead ECGs should be carried out prior to and as close as possible to having blood drawn. The 12-lead ECGs will be collected after the subject has rested in the supine position for at least 10 minutes. The allowed sampling window for 12-lead ECGs is ± 30 minutes from the nominal timepoint for all postdose 12-lead ECGs and no less than 10 minutes prior to dosing for predose 12-lead ECGs.
- f. Vital sign measurements (supine blood pressure [BP] and pulse rate) will be obtained at Screening and Check-in (Day -1), Day 1 (predose), Day 2 (predose, 2 hours after LOXO-305 dosing), Day 6 (predose and 2 hours after LOXO-305 dosing), Day 12 (predose, and 2 hours after LOXO-305 and repaglinide dosing), and EOT (Day 16, ie, 96 hours after LOXO-305 and repaglinide dosing on Day 12) or ET. When scheduled at the same time as blood draws, vital sign measurements should be carried out prior to and as close as possible to having blood drawn. BP and pulse rate will be measured using the same arm for each reading after the subject has been supine for at least 5 minutes. The allowed sampling window for vital sign measurements is ±30 minutes from the nominal timepoint for all postdose vital sign measurements and no less than 10 minutes prior to dosing for predose vital sign measurements.
- g. Oral temperature and respiratory rate will be obtained at Screening and Check-in (Day -1), and EOT (Day 16) or ET.
- h. Oxygen saturation will be measured via pulse oximetry once at Screening, Check-in (Day -1), predose on Day 1, and EOT (Day 16) or ET. The allowed sampling window for predose oxygen saturation measurements is no less than 10 minutes prior to dosing.
- i. An HDYF? inquiry will be performed at Screening (after the ICF is signed), at Check-in (Day -1), at each postdose vital sign measurement, and at an appropriate time for all other days.

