# 2.2. Secondary Objective

The secondary objective of the study is:

• to assess the safety and tolerability of multiple oral doses of LOXO-305 when administered alone and coadministered with repaglinide in healthy subjects.

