AEs and serious adverse events (SAEs) will be collected beginning at informed consent. AEs will be reported throughout the study (ie, from signing of the ICF until End of Study [EOS], or until ET if the subject discontinues from the study and does not complete a follow up phone call), either as subject medical history (if the event is reported as beginning prior to signing of the ICF or if the event occurs prior to study drug administration on Day 1 and is assessed as not related to study procedures by the Investigator [or designee]) or as AEs (if the event occurs after signing of the ICF but prior to study drug administration on Day 1 and is assessed as related to study procedures by the Investigator [or designee], or if the event occurs after study drug administration on Day 1 through EOT or ET regardless of relationship to study drug). From EOT or ET through EOS, only AEs assessed as related to study drug by the Investigator (or designee) are to be reported. All SAEs that develop from the time of ICF signing until EOS (or ET, if the subject discontinues from the study and does not complete a follow up phone call) are to be reported.

Study completion is defined as the time of the last subject's follow up.

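### The by-treatment TEAE tables set 10 days of LOXO-305 alone against a Day 12 column with about 4 days of all-causality reporting, and print no time at risk

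*SAP*

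**What the plan says.** SAP 8.6.1 assigns TEAEs to treatments by dosing day:

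- Repaglinide alone: "A TEAE occurring during or after Day 1 dosing and prior to Day 2 dosing will be assigned to 0.5 mg repaglinide".
- LOXO-305 alone: "A TEAE occurring during or after Day 2 dosing and prior to Day 12 dosing will be assigned to 200 mg LOXO-305".
- Combination: "A TEAE occurring during or after Day 12 dosing will be assigned to 200 mg LOXO-305 + 0.5 mg repaglinide". No end is given.

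The sentence introducing this list limits it to TEAEs judged related to study treatment. No rule is given for unrelated TEAEs. The same section nevertheless plans all-causality tables, "TEAEs (overall, serious, leading to discontinuation, and leading to death) by treatment", alongside tables of related TEAEs. Both report numbers of subjects and events. Neither reports time at risk.

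SAP 4 sets what is collected. An AE is reported "if the event occurs after study drug administration on Day 1 through EOT or ET regardless of relationship to study drug". After that, "From EOT or ET through EOS, only AEs assessed as related to study drug by the Investigator (or designee) are to be reported", while SAEs continue to be reported to EOS whatever their cause. Protocol Appendix 4 places EOT at "EOT (Day 16, ie, 96 hours after LOXO-305 and repaglinide dosing on Day 12) or ET". The follow-up call comes 7 ± 2 days later (Protocol 7.2.1).

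The secondary objective in SAP 2.2 is "to assess the safety and tolerability of multiple oral doses of LOXO-305 when administered alone and coadministered with repaglinide in healthy subjects".

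**The concern.** Every subject follows the same fixed sequence, so the three columns would have nearly the same number of subjects, and a reader will compare the percentages directly. The time behind them is not comparable. In the all-causality tables, LOXO-305 alone collects 10 days of events of any cause. The combination collects about 4 such days, then a period in which unrelated non-serious events are no longer reported. At an equal daily rate the combination column would be expected to look better simply because it was watched for less time, and some real increase in rate could be hidden.

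The two families of tables also use different effective windows under one column heading. In the related-TEAE tables the Day 12 column runs to EOS. In the all-TEAE tables it is a mixture of two reporting regimes. What is at stake is the AE evidence on LOXO-305 alone and coadministered. The primary PK analysis is not touched.

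**Working it through.** **Inputs from the documents**

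- Assignment boundaries: Day 1, Day 2 and Day 12 dosing (SAP 8.6.1).
- EOT: Day 16, 96 h after the Day 12 dose (Protocol Appendix 4).
- Follow-up after EOT: F = 7 days, range 5 to 9 (Protocol 7.2.1).
- Up to 16 subjects (Protocol 8.1).

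**Assumptions, not in the documents**

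- A constant daily TEAE rate within each window, continuing after EOT. Illustrations use 0.03 per subject-day on LOXO-305 alone, with 0.01 to 0.08 as the range.
- A share r of AEs judged related. Post-EOT unrelated SAEs are ignored.
- Windows treated as independent in the 16-subject comparisons.

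**Step 1. Windows.** (16 − 12) × 24 = 96 h, which reproduces the protocol's figure. The windows are 2 − 1 = 1 day, 12 − 2 = 10 days and 16 − 12 = 4 days of all-causality reporting. The first two add to 11 days, matching the stated washout. Protocol 1.6 gives 100 h for Day 16 instead of 96 h; this does not change the result. The related-only window from Day 12 is 4 + F = 9 to 13 days, nominally 11.

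**Step 2. Break-even rate ratio** (combination rate divided by LOXO-305-alone rate at which expected counts are equal). For the all-causality tables it is 10 / (4 + F × r). At F = 7:

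| Related share r | Calculation | Break-even |
|---|---|---|
| 0 (no post-EOT events) | 10/4 | 2.50 |
| 25% | 10/5.75 | 1.74 |
| 50% | 10/7.5 | 1.33 |
| 75% | 10/9.25 | 1.08 |
| 86% (6/7) | 10/10 | 1.00 |

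For related-only tables it is 10 / (4 + F): 10/9 = 1.11, 10/11 = 0.91 and 10/13 = 0.77. None of these ratios depends on the assumed daily rate.

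**Step 3. Expected share of subjects with at least one TEAE**, 1 − exp(−rate × effective days), at 0.03 per day:

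- LOXO-305 alone: 1 − exp(−0.30) = 25.9%.
- Combination, equal rate, counted to EOT only: 1 − exp(−0.12) = 11.3%.
- Combination, equal rate, related events after EOT added (7 days): 15.8% at r = 25% and 20.1% at r = 50%.
- Combination, doubled rate, to EOT only: 1 − exp(−0.24) = 21.3%, still below 25.9%.
- Combination, doubled rate, post-EOT events added: 29.2% at r = 25% and 36.2% at r = 50%, now above 25.9%.

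**Step 4. Sixteen subjects, exact binomial comparison, rates 0.01 to 0.08.**

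- Equal rates, to EOT only: the combination shows strictly fewer affected subjects with probability 0.60 to 0.93.
- Equal rates, r = 50%, 7-day follow-up: 0.46 to 0.65.
- Doubled rate, to EOT only: 0.44 to 0.61.
- Doubled rate, r = 50%, 7-day follow-up: 0.14 to 0.25.

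**Step 5. Effect of a denominator.** At 0.03 and 0.06 per day in 16 subjects, expected events to EOT are 0.03 × 10 × 16 = 4.8 and 0.06 × 4 × 16 = 3.84. Per subject-day, 4.8/160 = 0.03 and 3.84/64 = 0.06, so the true ratio of 2 is recovered.

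**The case against.** The strongest objection is that the Day 12 column, as planned, does not stop at EOT. Related AEs and all SAEs to EOS enter it, so a reader who infers that the tables hide any increase up to 2.5-fold has set those events to zero. The protocol's own healthy-volunteer summaries (Protocol 1.4.1) suggest a high related share: 3 of 3, 3 or 4 of 7, and 1 of 1, or 7 to 8 of 11 (64% to 73%). On a constant rate that gives a break-even of 1.18 to 1.10 at 7 days, and a doubled rate would then show as about 40% to 42% against 25.9%. This stands as a limit on size. It is not decisive the other way: the related share rests on 11 events, and a constant rate after EOT is doubtful about 5 half-lives after the last dose.

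Other points that stand:

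- The assignment rule covers related TEAEs only. Applying it to all TEAEs is an inference, though the SAP offers no other rule.
- These columns are not the only planned safety evidence. SAP 8.6.2 to 8.6.4 summarise laboratory, vital-sign and ECG data by treatment and timepoint, and AE listings carry onset time and duration.
- A simple events-per-day rate is not a clean remedy. SAP 8.6.1 counts a repeated preferred term once per treatment, which trims the longer LOXO-305 window more. The Day 12 window is one dose day plus washout, so an average over it can dilute an acute effect.

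It can also be said that safety is descriptive, with no inference planned (SAP 8.6.6), and that the window boundaries are printed. That lowers the importance. It does not make columns with different observation times comparable, and the reader would have to rebuild the denominators.

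**Conclusion.** The point holds for the all-causality by-treatment tables. With no time denominator, the combination column can read lower than LOXO-305 alone at an equal or somewhat higher daily rate. The break-even ratio is at most 2.5, and falls towards 1 as related post-EOT events enter the column: 1.74 at 25% related and 1.33 at 50%, assuming a constant rate and 7-day follow-up. The 2.5 follows from the calendar alone. The lower figures rest on the assumed related share and on the rate persisting off drug.

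Three stronger readings are not supported. The tables need not reverse a doubling: that depends on few or no post-EOT events. The imbalance does not extend to LOXO-305 alone against the combination in the related-only tables, where nominal windows are 10 and 9 to 13 days. The AE columns are not the whole of the safety assessment. The short repaglinide window (1 day) and the missing rule for unrelated TEAEs are further gaps that the same edit can close. This is a moderate reporting weakness in a descriptive secondary objective.

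**What to change.** In SAP 8.6.1 and the table shells:

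1. Keep n (%), and state that the assignment rule applies to all TEAEs, related or not.
2. Print subject-days at risk in each treatment column.
3. In the all-causality tables, end the combination column at EOT/ET and show post-EOT related AEs and SAEs on a separate line.
4. Add events per subject-day to the overall TEAE summary only, counting every event instead of one per preferred term.
5. Add a matched-window line with counts for the first 24 h after the Day 1, Day 11 and Day 12 doses. This gives equal time on repaglinide, LOXO-305 and the combination, and keeps an acute Day 12 effect visible.
6. State that LOXO-305 alone and coadministration will not be compared on the crude percentages alone.

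The cost is SAP and shell wording and a little programming. No new data are needed. The downside is that rates and 24-hour counts in up to 16 subjects are imprecise, above all for the 1-day repaglinide column. They remain descriptive and do not remove the effect of the fixed sequence.
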